## 9.2 SAMPLE SIZE DETERMINATION

In accordance with our power calculation, 15 participants are required to have a power of at least 0.8 with an alpha of 0.05, for expected changes in measures of endothelial function (pilot work, change in FMD in response to exercise pre =  $4.8 \pm 2.5$  %, post =  $2.7 \pm 1.7$ %) (FMD in rats in response to cannabis smoke, pre =  $7.5 \pm 2.5$ %, post =  $2.4 \pm 1.4$  %), artery stiffness (pilot work, change in PWV pre =  $7.4 \pm 1.3$  m/s, post (at rest) =  $6.0 \pm 1.3$  m/s) and cardiac function (pilot work, peak longitudinal strain: pre =  $-18.3 \pm 1.2$  %, post =  $-17.0 \pm 1.9$  %), therefore we will recruit 20 participants in each phase of the study to account for potential dropout.

## 9.3 POPULATIONS FOR ANALYSES

Only participants who complete all study procedures will be included for analysis of efficacy endpoints. All participants who consume cannabis at any time will be included in the analysis of safety endpoints.

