Continuous blood pressure, heart rate, and electrocardiogram monitoring will occur prior to, and during cannabis administration (prior to exercise) on all visits where cannabis is consumed. This procedure will be followed throughout the entirety of the 40-minute cannabis consumption period. If either systolic or diastolic blood pressure exceeds 160mmHg or 90mmHg at rest, respectively, exercise will not be performed, and the study visit will not continue. If heart rate exceeds 100bpm or falls below 40bpm at rest, exercise will not be performed, and the study visit will not continue.

All research will be performed within the department of Human Health and Nutritional Sciences at the University of Guelph.

There are no planned interim analyses planned for the current trial.

A sub-group analysis will be performed, with participants divided by sex, to determine the existence of any sex differences in primary and secondary endpoints.

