### 4.4 END OF STUDY DEFINITION

A participant is considered to have completed the study if he or she has completed either phase I or phase II of the study including the last scheduled procedure shown in the Schedule of Activities (SoA), Section 1.3.

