## 7 STUDY INTERVENTION DISCONTINUATION AND PARTICIPANT DISCONTINUATION/WITHDRAWAL

### 7.1 DISCONTINUATION OF STUDY INTERVENTION

If a participant experiences a cannabis-related severe adverse at any point during participation in the study, or new information regarding their health becomes available to them that would contraindicate cannabis use, they will be immediately discontinued from further trials. Investigators will inquire whether there have been any changes in health or prescription medication status each study visit. Severe cannabis related adverse events will be classified using the adverse event form, but will also by default include any instance of cannabis induced hyperemesis or any degree of psychosis. If a participant voluntarily withdraws, they will not be required to provide a reason, and no further data collection will occur. However, if a participant decides to withdraw following consumption of cannabis during a study visit, they will be required to remain in the laboratory for 4 hours following the moment of consumption, so that their safety may be monitored. Any adverse event that occurs will be recorded using an adverse event form.

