### 7.2 PARTICIPANT DISCONTINUATION/WITHDRAWAL FROM THE STUDY

Participants are free to withdraw from participation in the study at any time upon request. This includes during the inhalation procedure.

If a participant wishes to withdraw during or after the inhalation of cannabis they will be required to remain in the laboratory for the requisite recovery period of 4 hours. Each hour subjective effects, heart rate, and blood pressure will be measured.

An investigator may discontinue or withdraw a participant from the study for the following reasons:

- Pregnancy
- If any severe adverse event (AE), or other medical condition or situation occurs such that continued participation in the study would not be in the best interest of the participant
- If the participant reports meeting an exclusion criterion (either newly developed or not previously recognized) that precludes further study participation
- Participant unable to complete study procedures

The reason for participant discontinuation or withdrawal from the study will be recorded. Participants who discontinue the study will be replaced to ensure that the required pre-determined statistical power is met.

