### 8.3.7 REPORTING EVENTS TO PARTICIPANTS

Participants in this study will not be informed of any adverse events experienced by other participants. If the investigatory team discovers any incidental findings that suggest the participant seek medical attention, they will be informed immediately, and their participation in the study will be suspended until they have seen a physician. Only once they have obtained written permission from their physician, can they continue participation in the study.

---

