#### 9.4.2 ANALYSIS OF THE PRIMARY EFFICACY ENDPOINT(S)

All primary endpoints will be measured as continuous variables and will be repeated after each intervention performed on a given study visit. A one-way ANCOVA will be used to assess treatment effects. Covariates will include basic cardiovascular and haemodynamic variables that may confound primary endpoints. These covariates include heart rate, blood pressure, and pulse wave velocity. Results will be presented as adjusted means with standard deviations. Primary endpoints will only be analyzed for participants who complete the entirety of at least one phase of the proposed study. Missing data will be imputed using mean imputation from all other measurements collected from the given participant. Outliers will be included and excluded in independent analysis, both of which will be reported.

---

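### Filling each gap with the participant's mean over all other measurements biases contrasts between conditions, and no rule says how a stopped visit counts in the efficacy analysis

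*Protocol*

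**What the plan says.** **Missing values.** Protocol 9.4.2 (primary endpoints) and 9.4.3 (secondary endpoints), repeated in SAP 4.2 and 4.3, fill any missing value with the average of the same participant's other measurements. Neither document restricts that average to the same condition, to rest or exercise, or to values after consumption. Protocol 4.1 and 8.1 have FMD measured before and after consumption at each visit.

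**Efficacy set.** Protocol 9.3 and SAP 3: "Only participants who complete all study procedures will be included for analysis of efficacy endpoints". Protocol 9.4.2 and SAP 4.2: "Primary endpoints will only be analyzed for participants who complete the entirety of at least one phase of the proposed study". The latter fits the completion definition in Protocol 4.4, under which a participant has "completed either phase I or phase II of the study including the last scheduled procedure".

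**Stopped visits.** Protocol 4.1 monitors heart rate, blood pressure and ECG before and during consumption and adds: "If heart rate exceeds 100bpm or falls below 40bpm at rest, exercise will not be performed, and the study visit will not continue". A parallel sentence covers blood pressure. No section gives the analysis status of such a visit. The nearest provisions are these:
- 7.1 requires discontinuation for a severe cannabis-related event or new contraindicating health information; a breach of the limits is not listed.
- 7.2 lists "Participant unable to complete study procedures" as a reason for which an investigator may withdraw someone, and then: "Participants who discontinue the study will be replaced to ensure that the required pre-determined statistical power is met".
- 8.3.7 deals with suspension for an incidental finding: "Only once they have obtained written permission from their physician, can they continue participation in the study".
- Rescheduling is provided for a positive urine test (5.3) and a missed visit (7.3) only.

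**The concern.** The trial exists to compare conditions within a person. A fill-in value averaged over that person's other conditions pulls the missing condition towards the rest. Protocol 9.1 predicts that conditions differ: FMD falls after exercise and after smoking, and does not fall after vaporizing either product. On the plan's own hypotheses, then, the filled value is centred in the wrong place. It can shift the THC-versus-CBD contrast of Phase II away from a true zero, and shrink or inflate the smoking-versus-vaporizing contrast of Phase I.

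The stopped-visit gap bears on the same data. Protocol 9.1 expects cannabis to raise heart rate and systolic pressure (diastolic is predicted unchanged), so the variables that end a visit include ones the intervention is expected to move. With no stated rule, whether such a visit removes the participant, is repeated, or is kept and filled could be settled after the data are seen.

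**Working it through.** **Step 1: the plan's sample size.** Protocol 9.2 gives 15 participants for power of at least 0.8. Strain pilot: change 1.3, SDs 1.2 and 1.9. With a within-person correlation of 0.5 (assumed; not stated), the SD of change = √(1.2² + 1.9² − 2×0.5×1.2×1.9) = √2.77 = 1.664 and the standardised change = 1.3/1.664 = 0.781. A two-sided paired t-test at n = 15 then has power 0.803. The figure reproduces, and n = 15 is used below.

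**Step 2: the imputation shift.** With k of n values filled in one condition and m = k/n, expected shift in that condition's mean = m × (pool mean − true condition mean). It is zero only if the condition equals its pool.

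Phase II inputs, as FMD changes in percentage points:
- Exercise: 2.7 − 4.8 = −2.1 (pilot, Protocol 9.2).
- Vaporized THC and vaporized CBD at rest: 0 (9.1 predicts no decrease; taken as no change).
- THC+exercise and CBD+exercise: −2.1 each (exercise effect plus zero).
- Pre values: 0, five of them. The pre value at the exercise control visit is inferred.

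*Literal pool, THC+exercise missing:* pool = (−2.1 + 0 + 0 − 2.1 + 5×0)/9 = −0.467; shift = m × (−0.467 + 2.1) = 1.633m. The true THC+exercise minus CBD+exercise difference is 0.

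Noise scale: SD = √((2.5² + 1.7²)/2) = 2.14 from the FMD pilot SDs. With an assumed correlation of 0.5 the SD of a paired difference is also 2.14, and the standard error is 2.14/√15 = 0.55.

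| Values filled (of 15) | Apparent difference | In standard errors |
|---|---|---|
| 1 | +0.11 | 0.2 |
| 2 | +0.22 | 0.4 |
| 3 | +0.33 | 0.6 |
| 5 | +0.54 | 1.0 |

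If CBD+exercise is the missing condition the sign reverses. Equal gaps in both conditions cancel.

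*Post values only:* pool = −4.2/4 = −1.05, shift 1.05m, so 2, 3 or 5 filled values give +0.14, +0.21 or +0.35.

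*THC versus CBD at rest, THC missing, literal pool:* pool = (3×−2.1 + 0)/9 = −0.70, shift −0.70m, so −0.09, −0.14 or −0.23. The sign differs from the exercise contrast.

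**Step 3: Phase I** (smoking effect on FMD assumed −2.1 and additive; literal pool). The true smoking+exercise minus vaporizing+exercise difference is −4.2 − (−2.1) = −2.1.
- Smoking+exercise missing: pool = (−2.1 + 0 − 2.1 − 2.1)/9 = −0.70, shift 3.5m. With 2, 3 or 5 filled, 78, 67 or 44% of the difference remains.
- Vaporizing+exercise missing: pool = (−2.1 + 0 − 2.1 − 4.2)/9 = −0.933, shift 1.167m. The difference becomes 107, 111 or 119% of its true size.

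**Step 4: the stopped visit, if it makes a non-completer.** Every input is assumed: resting heart rate 65 ± 9 bpm, mean rise 10, 20 or 30 bpm, half the variance of the rise between persons, four Phase I cannabis visits, the upper heart rate limit only. By simulation:
- SD of rise 8: 5, 21 or 53% of participants have a stopped visit; those without one show 97, 94 or 90% of the true rise.
- SD of rise 12: 12, 32 or 61%, and 85, 83 or 79%.

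A primary endpoint is affected only through correlation. With a mean rise of 20 bpm (between-person SD 10, visit SD 5), an SD of FMD change of 2.21 and an assumed correlation of −0.3 to −0.5 between FMD change and heart rate rise, completers show a mean FMD change of about −1.9 to −1.8 against a true −2.1.

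**The case against.** **Size.** The illustration puts every gap in one condition. One or two filled values move the contrast by 0.2 to 0.4 of a standard error, and the planned ANCOVA covariates are not modelled. This stands. The shift is in expected value, and no false-positive rate has been shown.

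**Few gaps.** Phases are analysed separately, and within a completed phase 9.4.2 is no looser than 9.3. Unless stopped visits count as completed, the rule then reaches mainly lost or unusable readings. This also stands.

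**FMD is not every endpoint.** Protocol 8.1 describes echocardiography after consumption, and nerve activity is recorded at one visit only, so the pooling of pre values does not carry over to all endpoints. The pooling across conditions still applies to any endpoint measured under several conditions.

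**Stronger readings a reader might infer.**
- *That the completer rule is shown to bias the trial.* The documents do not say that a stopped visit makes a non-completer, and they give no heart rate rise, spread or stop rate. Withdrawal under 7.2 is discretionary. A stop before consumption does not depend on the acute response.
- *That selection and imputation bias add up.* For one stopped visit they are alternatives: a participant who is excluded is not filled, and one whose value is filled was not excluded.
- *That filled values are counted as real observations in the degrees of freedom.* The documents are silent on this.

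**Conclusion.** The imputation rule is wrong as written. It centres a filled value on a mixture of conditions that 9.1 expects to differ, so the contrast is biased in a direction set by which condition is missing. That conclusion needs only the wording of the rule and the plan's hypotheses. Its size is uncertain: about 0.1 FMD points per filled THC+exercise value in Phase II under the literal reading, which is small for one or two gaps and about one standard error for five of 15. The standard error rests on an assumed correlation of 0.5, and the Phase I figures on an assumed smoking effect.

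The completer point is a missing rule, not a demonstrated bias. The two wordings of the efficacy set need aligning, and the status of a stopped visit needs stating. If such a visit excludes the participant, heart rate effects are understated and replacement restores the number but not those responders; primary endpoints follow only if they correlate with the heart rate or blood pressure response. The plan should be changed on both counts; confidence is medium because the number of gaps and stops is unknown.

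**What to change.** 1. In Protocol 9.4.2 and 9.4.3 and SAP 4.2 and 4.3, delete the person-mean imputation. Analyse each phase with a repeated-measures mixed model, participant as random effect and condition as fixed effect, on all observed values.
2. In Protocol 9.3 and SAP 3, define the efficacy set for each phase as participants with at least one recorded post-intervention value for the endpoint, including values from participants later withdrawn or replaced.
3. Reconcile Protocol 4.1, 4.4, 7.2, 9.3 and 9.4.2, and SAP 3 and 4.2, on how a stopped visit is treated in the analysis. The stopping limits themselves are not in question here.
4. Report stopped visits by condition, and keep the completer analysis as a sensitivity analysis.

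Cost: no extra participants or procedures, but more than a wording change, because the primary model and the efficacy set both change. Numbers will be unequal across conditions. The mixed model relies on data being missing at random. It removes the imputation bias but does not fully remove bias from stops that depend on the response.

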### 1.3 SCHEDULE OF ACTIVITIES (SOA)

Procedure	Introductory Visit (Visit 0), Day 0	Exercise Control Visit (Visit 1), Day 7±1 day	Phase I Cannabis Visit (Visit 2), Day 14±1 day	Phase I Cannabis + Exercise Visit (Visit 3), Day 21±1 day	Phase I Cannabis Visit (Visit 4), Day 28±1 day	Phase I Cannabis + Exercise Visit (Visit 5), Day 35±1 day	Phase II Cannabis Visit (Visit 6), Day 42±1 day	Phase II Cannabis + Exercise Visit (Visit 7), Day 49±1 day	Phase II Cannabis Visit (Visit 8), Day 56±1 day	Phase II Cannabis + Exercise Visit (Visit 9), Day 63±1 day
Informed Consent	X									
Eligibility Questionnaire	X									
Physical Activity Readiness Questionnaire	X									
Height	X									
Weight	X	X	X	X	X	X	X	X	X	X
Blood Pressure and Heart Rate	X	X	X	X	X	X	X	X	X	X
Urine Test	X	X	X	X	X	X	X	X	X	X
Inquiry of Changes to Health and Prescription Status		X	X	X	X	X	X	X	X	X
VO 2 Max Test	X									
Pulse Wave Velocity		X	X	X	X	X	X	X	X	X
Brachial Artery FMD		X	X	X	X	X	X	X	X	X
Echocardiography		X	X	X	X	X	X	X	X	X
20 Minute Maximal Cycling Exercise		X		X		X		X		X
Vaporization of High THC Cannabis			X	X				X	X	
Smoking of High THC Cannabis					X	X				
Vaporization of High CBD Cannabis							X			X
Indirect Calorimetry/CPET	X	X		X		X		X		X
Microneurography (MSNA)			X							
Stress Echocardiography			X		X		X		X	
Measurement of Continuous Blood Pressure		X	X	X	X	X	X	X	X	X
ECG	X	X	X	X	X	X	X	X	X	X
Impedance Cardiography		X		X		X		X		X
Drug Effects Questionnaire			X	X	X	X	X	X	X	X

*This study will use a randomized crossover design. Phase I of this study will occur prior to the initiation of phase II. If a participant enters the study in phase II, but did not participate in phase I, they will be required to complete the introductory and exercise control visits. Visits 2-5 and 6-9 will occur in a randomized order, which will be individualized for each participant.*

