## 9.4 STATISTICAL ANALYSES

### 9.4.1 GENERAL APPROACH

Our study will be divided into two phases each of which will be analyzed independently. All tests of significance will be two-tailed, and statistical significance will be based upon an alpha error probability of 5% and a power for 80%. The data will be evaluated using both parametric and non-parametric tests, as applicable. If the data are found to be not normally distributed, the raw data will be transformed using an appropriate transformation model in order to perform the parametric assessments. Non-parametric tests will be performed on raw data. The data will be assessed as continuous and will be presented as means with standard deviations. A one-way analysis of covariance will be used to assess the treatment

effects (Phase I: exercise, vaporizing THC, smoking THC, vaporizing + exercise THC, smoking THC + Exercise, Phase II: exercise, vaporizing THC, vaporizing CBD, vaporizing + exercise THC, Vaporizing CBD + Exercise) on the primary endpoints. Covariates will be introduced into the models in order to assess the impact of certain potential factors on outcome, including fitness, blood pressure, resting heart rate, and any other factors that are observed during the study that appear to potentially influence the outcome.

Our secondary endpoints will be assessed using a repeated measures one-way ANOVA and paired t-tests. If there are significant interactions differences between pairs of means will be determined with a Bonferroni post-hoc test.

---

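### Two efficacy-inclusion rules conflict, and neither is tied to the phase being analysed

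*Protocol*

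**What the plan says.** - **Efficacy population (protocol 9.3, repeated in SAP 3).** "Only participants who complete all study procedures will be included for analysis of efficacy endpoints". No phase is named. The secondary-endpoint sections (protocol 9.4.3, SAP 4.3) contain no completion rule, so this sentence alone governs them.
- **Primary endpoints (protocol 9.4.2, repeated in SAP 4.2).** "Primary endpoints will only be analyzed for participants who complete the entirety of at least one phase of the proposed study". The phase that must be complete is not linked to the phase analysed.
- **Study completion (protocol 4.4).** "A participant is considered to have completed the study if he or she has completed either phase I or phase II of the study".
- **Unit of analysis (protocol 9.4.1).** "Our study will be divided into two phases each of which will be analyzed independently".
- **One-phase participation (note to the schedule, protocol 1.3).** "If a participant enters the study in phase II, but did not participate in phase I, they will be required to complete the introductory" visit and the exercise control visit. Joining Phase II alone is therefore allowed.
- **Missing data (protocol 9.4.2).** "Missing data will be imputed using mean imputation from all other measurements collected from the given participant". The rule is not limited to the same phase or condition.
- **Drop-outs (protocol 7.2).** "Participants who discontinue the study will be replaced to ensure that the required pre-determined statistical power is met".

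**The concern.** When phases are analysed separately, membership of a phase's efficacy set should depend on what the participant did in that phase. Neither rule does this, and they err in opposite directions for someone who takes part in both phases. Rule 9.3 lets an incomplete Phase II remove a complete Phase I. Rule 9.4.2, if it is what the analyst follows, lets a complete Phase I carry an incomplete Phase II into the Phase II analysis.

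Three things are at stake. Usable within-subject data may be thrown away in a small crossover. Partial records may enter with imputed conditions, possibly filled from the other phase. Primary and secondary endpoints of the same phase may rest on different people. Nothing in either document says which sentence prevails.

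**Working it through.** **1. The plan's own figure.** Protocol 9.2 requires 15 participants for 80% power at alpha 0.05; 9.4.1 makes tests two-sided. The binding input is peak longitudinal strain, −18.3 ± 1.2 before and −17.0 ± 1.9 after, a difference of 1.3. The pre-post correlation r is not given, so r = 0.5 is an assumption.

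- SD of the difference = √(1.2² + 1.9² − 2 × 0.5 × 1.2 × 1.9) = √2.77 = 1.664
- Standardised effect = 1.3 / 1.664 = 0.781
- Paired t-test (noncentral t): N = 15, power 0.803

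The figure of 15 is reproduced. It is sensitive to r: N = 26, 20, 18, 15, 13 and 11 at r = 0, 0.3, 0.4, 0.5, 0.6 and 0.7. Recruiting 20 per phase allows 25% loss, since 15 / (1 − 0.25) = 20.

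**2. Every participation pattern under each rule.** Entries are membership of the Phase I / Phase II analysis; a dash means the phase was not entered.

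| Phase I, Phase II | 9.3 read as both phases | 9.3 read as phases entered | 9.4.2 alone | Phase-specific |
|---|---|---|---|---|
| complete, complete | in / in | in / in | in / in | in / in |
| complete, partial | out / out | out / out | in / in | in / out |
| partial, complete | out / out | out / out | in / in | out / in |
| complete, not entered | out / – | in / – | in / – | in / – |
| not entered, complete | – / out | – / in | – / in | – / in |
| partial, partial | out / out | out / out | out / out | out / out |
| partial, not entered | out / – | out / – | out / – | out / – |
| not entered, partial | – / out | – / out | – / out | – / out |

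For people with one complete and one partial phase, neither reading of 9.3 nor 9.4.2 alone matches the phase-specific result. One-phase completers are lost only under the most literal reading of 9.3.

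**3. Illustration of size.** Assume the same 20 people enter both phases, all complete Phase I, m stop during Phase II and none is replaced.

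- 9.3: Phase I = 20 − m, Phase II = 20 − m
- 9.4.2 alone: Phase I = 20, Phase II = 20
- Phase-specific: Phase I = 20, Phase II = 20 − m

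With m = 5 the Phase I sets are 15, 20 and 20, and the Phase II sets are 15, 20 and 15. With m = 1 the only change is 19 in place of 15. With m = 6, rule 9.3 leaves 14 in Phase I, below the planned 15, although all 20 finished that phase.

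**4. What the lost Phase I records cost.** Strain power at 15 against 20 participants is 0.80 against 0.91 at r = 0.5, 0.69 against 0.82 at r = 0.3, and 0.93 against 0.98 at r = 0.7. These are paired-t figures, used as a guide and not as the power of the planned ANCOVA. They do not carry over to the Phase II set of 20 under 9.4.2, because 5 of those records are incomplete.

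**The case against.** The best reply is that both sentences are restrictions. Each says who may be analysed at most, so both apply and the stricter one, 9.3, governs. A Phase I completer who stops in Phase II then fails 9.3, and the partial record never enters. This is a fair reading, and it means that retention of a partial phase depends on letting 9.4.2 override 9.3. But it does not rescue the plan. Anyone who passes 9.3 on either reading also passes 9.4.2, so the 9.4.2 sentence would have no effect, and 9.3 would still discard the finished Phase I.

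Replacement of drop-outs (7.2) limits the loss of numbers. It does not say who is analysed, and a replacement recruited into Phase II alone does not restore the Phase I data that 9.3 drops. Nor do the documents say that imputation extends to whole visits never attended after withdrawal; the wording simply does not exclude it.

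Some stronger readings are tempting but not supported:

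- *Three conflicting definitions.* Section 4.4 sets the same condition as 9.4.2 in other words, and it defines study completion, not an analysis set. There are two rules.
- *Both analyses could be emptied if nobody does both phases.* This needs the most literal reading of 9.3, which would defeat 1.3, 4.4, 9.2 and 9.4.1 together. No overlap figure is given; 20 participants in the synopsis and 20 per phase in 5.5 would fit a large overlap.
- *A failed microneurography recording removes a participant from every endpoint.* The imputation rules presuppose missing measurements among those included, and 5.5 pays those who complete that session, which suggests that not everyone is expected to.
- *The rule will be chosen after results are seen.* Section 6.3 blinds investigators to condition during analysis, and 9.4.6 says Phase I results will not alter the planned Phase II analyses. The documents show only that the rule is not fixed.

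**Conclusion.** The concern holds as a conflict between two rules, each copied into the SAP. The retention problem arises only for people who enter both phases and rests on 9.4.2 being followed by itself. The loss of a finished phase arises under 9.3 on either reading. A participant who enters one phase and stops partway is excluded under every rule, so that case is not in dispute.

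The size cannot be fixed from the documents because the overlap between phases and the drop-out pattern are not given. Under the stated illustration, the choice of sentence moves each phase's N between 15 and 20. A phase-by-phase intention may be inferred from 4.4 and 9.4.1, but it is not written. The sample-size figure of 15 does not change.

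**What to change.** In protocol 9.3, 9.4.2 and 9.4.3 and in SAP 3, 4.2 and 4.3, define one efficacy set per phase and use it for primary and secondary endpoints alike. Suggested wording: *The efficacy set for a phase consists of participants who complete the four experimental visits of that phase and the exercise control visit (Visit 1), regardless of participation in the other phase.*

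This replaces both existing completion conditions. Visit 1 has to be named because the schedule labels it with neither phase, while 4.1 requires it for each and 9.4.1 uses its exercise condition in both. Add that the single-visit microneurography recording does not determine membership for the other endpoints.

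Whether a completer set is the right choice at all is a separate question. The change needs no new data or participants, only an amendment to the wording, and should be in place before Phase I is analysed.
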